#### **6.3.2. Week 4 and Week 12**

Subjects should be instructed to fast from food and non-clear liquids on the evening prior to the visit to ensure a minimum 8-hour fast prior to the fasted blood sample collection.

The Schedule of Study Procedures is summarized in [Table 1](#).

#### **6.3.3. Weeks 24, 36, 48, 60, 72, 84, 96, 108, 120, 132, 144**

Subjects should be instructed to fast from food and non-clear liquids on the evening prior to the visit to ensure a minimum 8-hour fast prior to the fasted blood sample collection.

The Schedule of Study Procedures is summarized in [Table 1](#).

#### **6.3.4. Weeks 52, 104, and 156 (1 year, 2 year and 3 year)**

The Schedule of Study Procedures is summarized in [Table 1](#).

### **6.3.5. Early Study Drug Discontinuation**

Subjects who prematurely discontinue the Study drug prior to 3 years completion due to AEs, loss of response, lack of efficacy or any other reason besides withdrawal of consent during the LTS Study will be asked to return for an Early Study Drug Discontinuation visit. This visit will be conducted within 5 days after the last dose of Study drug.

Subjects should be instructed to fast from food and non-clear liquids on the evening prior to the visit to ensure a minimum 8-hour fast prior to the fasted blood sample collection.

Subjects will also return for the End of Study visit for collection of safety data and assessment of disease activity.

The Schedule of Study Procedures is summarized in [Table 1](#).

### **6.3.6. End of Study (EOS)**

An EOS visit will be required for all subjects 4 weeks following their last dose of Study drug. Subjects should be instructed to fast from food and non-clear fluids on the evening prior to the EOS visit to ensure a minimum 8-hour fast prior to the fasted blood sample collection.

The Schedule of Study Procedures is summarized in [Table 1](#).

## **6.4. Description of Study Assessments**

### **6.4.1. Demographic and Baseline Assessments**

#### **6.4.1.1. Informed Consent, Demographics, and Inclusion/Exclusion Criteria**

Written informed consent must be obtained, signed, and dated after the nature of the Study has been explained to the subject and before any Study procedure is performed.

Demographic data may be collected from the Protocol 0157, if applicable.

Inclusion and exclusion criteria will be assessed at Day 1 prior to entry into the LTS Study. Subjects will only be eligible for enrollment into the Study if they meet all of the inclusion and none of the exclusion criteria.

#### **6.4.1.2. Medication History**

On Day 1 of the LTS Study, all concomitant medications will be reviewed with the subject, if applicable. Protocol 0157 medications ongoing at the time of Day 1 of the Protocol 0164 LTS Study may be collected from the Protocol 0157, if applicable.

Please refer to Inclusion/ Exclusion Criteria and [Appendix 4](#) for Prohibited Medications.

#### **6.4.1.3. Medical History**

Medical history and adverse events may be collected from the Protocol 0157, if applicable.

#### **6.4.1.4. Body Weight**

Weight measurement (in kg and without shoes) will be obtained according to the Schedule of Study Procedures ([Table 1](#)).

#### **6.4.1.5. Smoking Status**

Subject's current use of tobacco, number of years used, and annual pack years used will be obtained according to the Schedule of Study Procedures (Table 1).

#### **6.4.1.6. Vital Signs**

Heart rate (HR), systolic and diastolic blood pressure (BP), respiratory rate, and body temperature will be recorded according to the Schedule of Study Procedures (Table 1).

Blood pressure and heart rate will be measured after the subject has been resting for at least 5 minutes in the seated or supine position. Subject position, measurement device, and arm (left vs. right) should be kept consistent throughout the Study. Blood pressure will be measured using a manual or automatic blood pressure device. Heart rate will be recorded by palpation of the radial pulse over at least a 30-second period or by the automated blood pressure device.

Body temperature will be measured and reported in degrees Celsius. The method used to collect temperature needs to be consistent throughout the subject's participation.

Any vital sign outside the normal range may be repeated at the discretion of the investigator. The vital sign measurements (BP and HR) should be performed after the subject has rested sufficiently as determined by the appropriate site staff. Collection of additional vital sign measurements for routine safety monitoring at additional time points or Study days may be performed at the discretion of the investigator, or upon request by the Sponsor.

#### **6.4.1.7. 12-Lead Electrocardiograms**

Interpretable ECG recordings (e.g., without artifacts) will be obtained according to the Schedule of Study Procedures (Table 1). Twelve-lead safety ECGs will be collected in singlet at each scheduled time point.

ECGs must be performed after the subject has been resting in a supine position for at least 10 minutes.

For monitoring purposes, the investigator must review, provide interpretation for ECG recordings other than sinus rhythm on the ECG tracing, sign, and date all safety ECG tracings. Paper copies of ECG tracings will be kept as part of the subject's Study file at the site.

If at a particular post dose time point, the QTcF is > 500 msec and/or 60 msec longer than the value at Day 1 or the mean QRS interval is > 130 msec, a decision on Study drug discontinuation should be made by the investigator with input from the Study Medical Monitor, if feasible. The investigator should also consider evaluating the subject for potential concurrent risk factors (e.g., electrolyte abnormalities, concomitant medications known to prolong the QT interval, severe bradycardia).

Results from a plasma TD-1473 exposure QTc analysis of data obtained from the SAD and MAD Study in healthy subjects and preclinical data were used in considering frequency and replicate ECGs required for this Study.

#### **6.4.1.8. Physical Examination**

The physical examination will be performed by a physician, nurse practitioner, physician's assistant, or equivalent, according to local practice standards, at each scheduled time point as specified in the Schedule of Study Procedures ([Table 1](#)).

Completion of additional physical examinations for routine safety monitoring at additional time points or Study days may be performed at the discretion of the investigator, or upon request by the Sponsor. A physical exam of the organ system associated with any reported AE, even if resolved, should be performed at subsequent Study visits.

#### **6.4.1.9. Concomitant Medications / Treatments**

All concomitant medications (i.e., prescription and over-the-counter medications, herbals, vitamins, and supplements) will be reviewed throughout the Study as described in the Schedule of Study Procedures ([Table 1](#)). Details such as name of medication, date started and stopped, route of administration, indication, and dose will be recorded. Medical therapy may be altered during the study however administration of a prohibited medication/ treatments listed in [Appendix 4](#) should result in the subject being discontinued from the Study.

Refer to [Section 6.5](#) for further details.

#### **6.4.1.10. Adverse Events (AEs)**

Adverse events, including serious adverse events (SAEs) and adverse events of special interest (AESI) will be reviewed and recorded following the time the subject signed the Informed Consent Form through the follow-up visit. AEs may be observed by the site Study personnel or spontaneously reported by the subject or reported in response to standard questions from site Study personnel. Subjects will be reminded to call the site to report AEs that occur between visits. Refer to [Section 6](#) for definition, assessment, and reporting of AEs.

#### **6.4.1.11. Pregnancy Test (females of child-bearing potential only)**

Urine b-hCG testing will be performed during specified visits, as listed in the Schedule of Study Procedures ([Table 1](#)), before study drug dosing, on females of childbearing potential to confirm the absence of pregnancy. If the urine b-hCG test is positive, a serum b-hCG test must be performed. The pregnancy test must be confirmed negative for a subject to be eligible for this Study unless the PI deems the test is falsely positive.

Detailed instructions and collection kits for sample collection, handling, and shipping will be provided by the central laboratory.

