**Inclusion Criteria:**

To be eligible for the study, subjects are required to enter the LTS Study within 14 days of exiting the Maintenance Study of Protocol 0157 and must meet all the following criteria:

1. One of the following:
  - a. Those who demonstrated persistent (as confirmed by endoscopy) loss of response (no improvement approximately 6 to 8 weeks after meeting loss of response criteria)  
**OR**
  - b. Two Clinical Flares after an episode of loss of response (as confirmed by endoscopy) during the Maintenance Study.  
**OR**
  - c. Those who have completed the Maintenance Study (even if the subject declined endoscopy during a clinical flare assessment during the Maintenance Study of Protocol 0157) and have a confirmed clinical remission status (in remission or not in remission) with available results
2. During the study and for 7 days after receiving the last dose of the study drug, females of childbearing potential or men capable of fathering children must agree to use highly effective birth control measures (failure rate <1% when used consistently and correctly) or agree to abstain from sexual intercourse. Females of childbearing potential must test negative for pregnancy at Day 1 (Refer to [Section 4.3](#)).
3. All male subjects must agree to refrain from semen donation during the study and for 7 days after the last dose of study drug.

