**Coexisting medical conditions or past medical history:**

6. Deemed by the investigator to be inappropriate for this study; or has any condition which would confound or interfere with the evaluation of the safety or tolerability of the study drug [e.g., developed unstable or uncontrolled and clinically significant allergic (except for untreated, asymptomatic, seasonal allergies), hematological, endocrine/metabolic, coagulation, immunologic, pulmonary, cardiovascular, hepatic (except hepatic steatohepatitis), GI (except UC), genitourinary, psychiatric, oncologic thrombotic (e.g., deep vein thromboses (DVT) or pulmonary embolism or neurological disease or other medical disorder before during or after Protocol 0157)]; or is unable or unwilling to comply with the study protocol.
7. Develops hypersensitivity to excipients or contents of the study drug as noted in Protocol 0157.
8. Participating in or interested in participating in another investigational study (exception Protocol 0157)
9. Has clinically significant abnormalities in the results of laboratory evaluations at the most recent laboratory evaluation prior to LTS Day 1 visit as determined by the investigator, including:
  - AST, ALT, or alkaline phosphatase  $\geq 2x$  the upper limit of normal (ULN)
  - Total bilirubin  $> 2x$  ULN (unless diagnosis of Gilbert's syndrome)
  - Creatinine clearance as calculated by the Cockcroft-Gault formula  $< 30$  mL/min (Refer to [Appendix 2](#))
  - Total white blood cell count (WBC)  $< 3 \times 10^9/L$
  - Absolute neutrophil count  $< 1.5 \times 10^9/L$
  - Absolute lymphocyte count  $< 0.8 \times 10^9/L$
  - Hemoglobin  $< 8$  g/dL
  - Platelet count  $< 100 \times 10^9/L$ .
10. Subject has had a live viral vaccine (e.g., MMR, varicella zoster, herpes zoster, oral polio virus, FluMist®, attenuated typhoid fever vaccine, attenuated rotavirus vaccine, yellow fever vaccine, or any investigational live vaccine) within 4 weeks prior to Day 1 and/or is unwilling or unable to avoid live viral vaccines during the Study and for 8 weeks following the last dose of study drug. Subject must be willing to avoid contact with any

household member who has been vaccinated with a live attenuated vaccine within 2 weeks after vaccination.

11. Are pregnant, lactating, breastfeeding or planning to become pregnant during the Study or within 7 days after the last dose of Study Drug

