#### **4.3. Women of Childbearing Potential (WOCBP) and Acceptable Birth Controls**

Women of childbearing potential must have documentation of a negative pregnancy test at Day 1 and prior to dosing. All female subjects of childbearing potential must agree to abstain from sexual intercourse or to use a highly effective method of birth control during the study and for at least 7 days after completion of Study drug dosing.

Females are considered not of childbearing potential if they have had a total hysterectomy and/or bilateral tubal ligation or hysteroscopic sterilization (documentation for surgeries must be provided before randomization) or are in a postmenopausal state (i.e., females who have had cessation of prior occurring menses for  $\geq 24$  months without alternative causes or females with premature ovarian failure).

Follicle-stimulating hormone (FSH) will be tested at Day 1 in post-menopausal females only to confirm post-menopausal state.

Highly effective birth control methods are defined as methods that can achieve a failure rate of less than 1% per year when used consistently and correctly. Such methods include: combined (estrogen and progestogen containing) hormonal contraception associated with inhibition of ovulation (oral/intravaginal/transdermal); progestogen-only hormonal contraception associated with inhibition of ovulation (oral/injectable/implantable); intrauterine device; intrauterine hormone-releasing system (IUS); bilateral tubal occlusion; vasectomised partner; sexual abstinence (if this is in line with the preferred and usual lifestyle). Vasectomised partner is a highly effective birth control method provided that partner is the sole sexual partner of the WOCBP trial participant and that the vasectomised partner has received medical assessment of the surgical success. Sexual abstinence is considered a highly effective method only if defined as refraining from heterosexual intercourse during the entire period of risk associated with the study treatments. More restrictive methods of birth control may be required as per local country requirements, and this will be defined in the IRB/IEC approved subject informed consent form.

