- a. Subject will be enrolled into the Protocol 0164 (LTS) and undergo treatment-assignment on Day 1 after subject has signed informed consent and is confirmed to be eligible for the study. **Note:** the first visit of Protocol 0164 (LTS) is Day 1 and will include Study Drug intake. Subjects exiting Protocol 0157 who have already taken Study drug from Protocol 0157 will need to return to the Clinic on another day prior to consenting to LTS in order to ensure that they are able to take LTS Day 1 Study Drug in clinic. Subjects **should not** receive Protocol 0157 Study Drug AND Protocol 0164 (LTS) Study Drug on the same day. Day 1 of Protocol 0164 (LTS) should be within 14 days of subject exiting the Maintenance Study. If any listed study procedure has been completed in the last 14 days in the Protocol 0157 prior to Day 1, it does not need to be repeated during Protocol 0164 (LTS) Day 1.
- b. Medical history information, AE's and partial Demographic data will be collected from the Protocol 0157 database, if applicable. Additional demographic data may be required to be entered into the Protocol 0164 (LTS) database.
- [REDACTED]
- [REDACTED]
- e. Urine b-hCG testing will be done before every visit for women of childbearing potential to confirm absence of pregnancy before dispensation of study drug. If the urine b-hCG test is positive, a serum b-hCG test must be performed.
- [REDACTED]
- g. Study drug will be dispensed for subjects to administer daily at home **with the exception** of Week 156 which is the last treatment visit.
- h. Subjects will continue to complete the electronic diary **on a daily basis for the initial 12 weeks** of the LTS. Subjects will be instructed on daily diary completion, including symptom monitoring (rectal bleeding and stool frequency) as well as study drug dosing details from Day 1 through to Week 12. Subjects will be counseled on missed diary entries and missed study drug doses. Subjects will return the electronic diaries at Week 12.
- i. After Week 12 subjects will be contacted approximately 10 days ±2 days preceding each clinic visit to be reminded that they will be asked to recall their symptoms (rectal bleeding, bowel movements and study drug dosing) for the 7 days prior to clinic visit.

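### Protocol 6.4.1.11 lets the investigator waive a confirmed negative pregnancy test that inclusion criterion 2 and Section 4.3 require without exception

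*Protocol*

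**What the plan says.** Protocol Section 6.4.1.11 sets out urine testing with a serum follow-up: "If the urine b-hCG test is positive, a serum b-hCG test must be performed". It then states the eligibility rule. The pregnancy test "must be confirmed negative for a subject to be eligible for this Study unless the PI deems the test is falsely positive".

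The eligibility sections are stricter. Inclusion criterion 2, in the Synopsis and again in Section 4.1, reads "Females of childbearing potential must test negative for pregnancy at Day 1". Section 4.3 adds documentation and timing: "Women of childbearing potential must have documentation of a negative pregnancy test at Day 1 and prior to dosing". Section 6.4.1.1 makes the criteria binding as a set: "Subjects will only be eligible for enrollment into the Study if they meet all of the inclusion and none of the exclusion criteria". Exclusion criterion 11 separately bars women who "Are pregnant, lactating, breastfeeding or planning to become pregnant during the Study or within 7 days after the last dose of Study Drug".

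The SAP's copy of the visit schedule (Section 1.4, Table 4, footnote e) repeats the serum step, with testing to be done "before dispensation of study drug. If the urine b-hCG test is positive, a serum b-hCG test must be performed". It mentions no investigator exception. That footnote is marked on the visits after Day 1.

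**The concern.** The protocol gives two answers to the same eligibility question. Take a woman of childbearing potential whose Day 1 test is positive, who has no negative result on file, and whose investigator believes the positive is false. Section 6.4.1.11 makes her eligible. Inclusion criterion 2 and Section 4.3 do not.

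Eligibility leads directly to exposure, because Section 5.2 has the first dose taken in the clinic on Day 1. The test is the objective check behind the exclusion of pregnant women. The exception replaces that check with judgment in exactly the women whose test came back positive. It asks for no repeat test, no contact with the medical monitor and no written reason. If the judgment is wrong, the result is the embryo-fetal exposure that the Day 1 test is there to prevent.

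There is also a conduct problem. It is unclear whether such an enrollment is permitted or is a protocol deviation.

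**Working it through.** No arithmetic applies and the plan gives no figure to reproduce. The check compares the rules and asks when the exception changes the outcome.

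**The rules**

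- Inclusion criterion 2 (Synopsis and Section 4.1): a negative Day 1 test, no exception. The Synopsis restates Section 4.1, so this is one rule stated twice.
- Section 4.3: a documented negative test at Day 1 and before dosing, no exception.
- Section 6.4.1.1: every inclusion criterion must be met, and no waiver route is given.
- Section 6.4.1.11: serum test after a positive urine test; confirmed negative required, or else the investigator's judgment that the positive is false.

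**When the exception matters**

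The table assumes that the investigator deems any positive result false, and that a negative serum result counts as a confirmed negative.

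| Urine | Serum | 6.4.1.11 without the exception | 6.4.1.11 as written | Criterion 2 and Section 4.3 |
|---|---|---|---|---|
| Negative | Not needed | Eligible | Eligible | Met |
| Positive | Negative | Eligible | Eligible | Met by the serum result |
| Positive | Positive or equivocal | Not eligible | Eligible | Not met |
| Positive | Not yet available | Not eligible | Eligible | Not met |

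In the first two rows the exception changes nothing. It alters the outcome only in the last two, where no negative result exists, and those are the rows in which Section 6.4.1.11 contradicts the other two rules.

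**Could another provision reconcile them?**

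- Exclusion criterion 11 concerns pregnancy itself, not the test result. It limits the harm but does not settle which testing rule governs.
- Footnote a of the schedule (SAP Section 1.4) lets a procedure done in Protocol 0157 within the 14 days before Day 1 stand in for the Day 1 procedure. That affects the timing of the test and creates no false-positive exception.
- Footnote e covers later visits and so does not decide eligibility. It does show that the text on later dispensing has no exception, while the text on entry has one.

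The operative sentences are not redacted: the redactions in Section 4.1 fall in criterion 1, not criterion 2.

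**The case against.** The best counter-argument is a milder reading. Section 6.4.1.11 speaks of the test in the singular, so the exception might address a discordant pair: urine positive, serum negative, and the investigator sets the urine result aside. A negative result would then be on file and Section 4.3 would be satisfied. The reading is possible, and it may be what was intended, but the sentence does not say it. It offers the investigator's judgment as an alternative to a confirmed negative and does not require a negative serum result. In the discordant case the exception is not needed at all. If that was the intent, the correction below simply states it.

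Several other points bear on severity, and they stand:

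- A site that follows criterion 2 and Section 4.3 would not dose the woman described. Contraception or abstinence is required, testing recurs at later visits, and Section 6.7 stops drug immediately on pregnancy.
- Section 1.5 describes TD-1473 as not genotoxic. It reports no evidence of direct embryo-fetal toxicity or teratogenicity up to 1000 mg/kg/day in rats and 60 mg/kg/day in rabbits, and no measurable drug in fetal blood in treated animals. This does not justify dosing a pregnant woman, but it tempers the expected harm.
- SAP Section 1 says the study was terminated early, with all last doses by 09SEP2021. Correction now protects no further subject in this study.

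It can also be said that a sponsor may choose to let investigators resolve false positives. It may, but the choice would then have to appear in criterion 2 and Section 4.3 with the evidence required. As it stands, those sections contradict it.

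**Conclusion.** The concern holds. Section 6.4.1.11 conflicts with two distinct eligibility rules, one of which is stated twice, and its exception has effect only when there is no negative result. This conclusion rests on treating a negative serum result after a positive urine test as a confirmed negative, which is the natural purpose of the serum step.

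The practical reach is narrow. Only women with a positive test whom the investigator judges not to be pregnant are affected. The documents give no count or rate, and few are to be expected. Harm requires a wrong judgment. No endpoint, analysis set or summary changes. This is a subject-safety and consistency defect that should be corrected, not a threat to the analysis.

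**What to change.** In Protocol Section 6.4.1.11, delete the exception for a result that the investigator considers falsely positive. State instead that, when the urine test is positive, a negative serum b-hCG result must be on file before the first dose. Criterion 2, Section 4.3 and exclusion criterion 11 can stay as they are.

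The change is one sentence. The serum test is already mandatory after a positive urine test, so no procedure is added. The first dose may have to wait for the serum result, but Section 4.3 already implies that wait. The real cost falls on a rare woman whose serum result is truly a false positive. She would be delayed, and excluded if the delay passes the 14-day entry limit in Section 4.1. She already fails criterion 2 and Section 4.3, so the edit removes no eligibility that those sections give her.

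Because dosing has ended, the sponsor can also check whether any woman was enrolled under the exception and, if so, report it.
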